1. LIST OF ABBREVIATIONS

Table 1: List of Abbreviations

Aβ	Amyloid-β
Aβ+	Amyloid positive, AD-like
Aβ-	Amyloid negative, not AD
AD	Alzheimer's disease
CERAD	Consortium to Establish a Registry for Alzheimer's Disease
CN	Cognitively Normal
CRF	Case report form
PET	Positron emission tomography
SD	Standard deviation
SE	Standard error
SUVR	Ratio of standardized uptake values

2. INTRODUCTION

Alzheimer's disease (AD) is the most common cause of dementia in the elderly, affecting more than 4 million people in the United States alone. However, diagnosis and treatment of the disease have been hampered by the absence of reliable non-invasive markers for the underlying pathology.

Florbetapir F 18 is well-tolerated imaging tracer, that has an acceptable radiation dosimetry profile at the proposed injected dose level of 370Mq (10mCi) and can distinguish patients with AD from normal subjects, and may be useful for the detection of amyloid plaque pathology in the brains of living subjects. This protocol has been developed to allow non-Avid investigator initiated studies to incorporate florbetapir F 18 in their protocol. The purpose of this statistical analysis plan (SAP) is to describe the statistical methods used in safety evaluation of subjects who exposed to florbetapir injection under this protocol. This SAP should be read in conjunction with protocol.

3. STUDY OBJECTIVES

The specific objectives of this protocol were to expand the safety database of florbetapir F 18 PET imaging safety, amyloid binding, and long-term outcome, and to provide standardized conditions for florbetapir F 18 use, data collection, and analysis in other studies (companion protocols). This SAP will only assess the safety of florbetapir. Imaging assessments for the study population were scientifically interesting at the time the study was initiated, but are no longer relevant to the field, as the efficacy of the companion studies, as well as other efficacy studies, have been extensively published in the academic literature.

4. STUDY DURATION AND VISIT SCHEDULE

The following flow chart describes the study duration and visit schedule:

Evaluations	Screen	Pre-dose	Dose	Injection Circulation (0 – 50 minutes) ³	Continuous PET Imaging 10 minutes	End of Imaging	24-72 hours post injection
Signed Consent	X						
Medical / Disease History	X						
Concomitant Meds	X	X					
MMSE	X						
Physician Visit	X	X ¹				X ¹	
Vital Signs		X					
Urine Pregnancy Test	X	X					
Florbetapir F 18 Administration			X				
PET Imaging ²					Continuous 10 minute scan - 50 minutes after dose injection		
Follow-up Phone Call							X
Adverse Event Assessment	X	X	X	X	X	X	X ³

5. CLINICAL ASSESSMENTS

5.1. Screening and Baseline Assessments

There are many clinical assessments data collected in companion protocols. For the safety evaluation purpose of this protocol, the following screening and baseline assessments will be included:

- 1). Subjects' birth year, sex, race, ethnicity, and education;

5.2. Image visit Assessments

AE, and/or SAE; vital signs: immediate prior to injection, and at the end of study visit, prior to discharge (approximately 50 minutes after florbetapir F 18 administration).

5.3. Follow up

A follow-up phone call to the subject (or the caregiver as appropriate) will be conducted approximately 24-48 hours after the imaging session to confirm their well-being and query them about any new adverse events.

6. GENERAL CONSIDERATIONS

Study day is calculated as assessment date minus date of study drug (florbetapir) administration + 1. Date of florbetapir administration is defined as study day 1.

Individual data will be displayed in listings sorted by subject identification number. The subject identification number is a combination of the site number and the subject number.

Continuous data will be summarized using the following descriptive statistics: number of subjects (n), mean, standard deviation (SD), median, minimum (min), and maximum (max). Categorical data will be summarized using the number (n) and percentage (%) of subjects for each category. When count data are presented, the percent will be suppressed when the count is zero in order to draw attention to the non-zero counts. The denominator for all percentages will be the number of subjects in that treatment group within the population of interest unless otherwise specified.

All analyses will be conducted using SAS® Version 8.2 or higher.

6.1. Analysis Populations

6.1.1. Enrolled Population

Not all subjects enrolled in companion protocol would receive a florbetapir scan. The purpose of this protocol is to evaluate the safety of florbetapir, therefore the enrolled population will not be defined in this SAP. The disposition table will summarize the study subjects based on safety population.

6.1.2. Efficacy Population

No efficacy analyses will be performed, hence no efficacy population is defined for this safety report.

6.1.3. Safety Population

The safety population will consist of all subjects who received at least one injection of florbetapir ¹⁸F. All safety endpoints will be summarized using the safety population.

7. SUBJECT DISPOSITION AND ELIGIBILITY CRITERIA

Disposition of subjects including the number and percentage of subjects will be displayed based on Safety population. Since there no efficacy analysis planned for this protocol, the efficacy population will not be included in the disposition table.

A listing will present subject disposition data.

8. BASELINE PATIENT DATA

8.1. Baseline Demographic and Physical Characteristics

Frequency distributions and summary statistics for demographic and baseline characteristics will be presented all subjects in the Safety population.

Demographics and baseline characteristics will be also presented in listings.

8.2. Concomitant Medications

Due to the consideration that this protocol is focus on safety evaluation of florbetapir F18, the concomitant medications are not be presented. If concomitant medications are needed to explain safety findings, tables and listings will be generated post hoc.

9. EFFICACY

This SAP will only assess the safety of florbetapir F18 by examining reported adverse events for the study. Imaging assessments for the study population were scientifically interesting at the time the study was initiated, but are no longer relevant to the field, as the efficacy of the companion studies have been extensively published in the academic literature.

10. SAFETY AND TOLERABILITY

All safety analyses will be conducted using the safety population.

10.1. Adverse Event Preferred Term and Body/Organ System Summary Tables

In this study, an Adverse Event (AE) is defined as any undesirable experience occurring to a subject after an injection of florbetapir F 18, whether or not it is considered as related to the investigational product. Laboratory test abnormalities considered by the Investigator to be clinically relevant should be reported as AEs. For this protocol, treatment-emergent AEs (TEAE) are considered as any undesirable experiences, signs, or symptoms that begin or worsen in intensity or frequency at the time of or after the administration of study drug, and within 48 hours since study drug injection. These will be recorded on the AE pages.

The incidence of AEs will be presented overall by system organ class (SOC) and by preferred term. Incidence of AEs by severity and relationship to study medication will also be presented. Adverse events resulting in discontinuation from the study and the incidence of serious adverse events (SAE) will be summarized.

Pre-existing conditions (i.e., undesirable experiences, signs, or symptoms that begin prior to the Screening Visit) will be recorded on the medical history and/or physical exam pages and will not be summarized in this study.

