- With prior sponsor approval and at the discretion of the investigator, a subgroup of not more than 5 subjects will be given the option of having a regimen of arterial blood sampling with up to 70 minutes of imaging beginning immediately after florbetapir F 18 administration. See Appendix 11.4 for detailed instructions on arterial blood sampling;
- Subjects will be observed continuously for signs of adverse events or serious adverse events;
- The injection site will be observed for excessive inflammation or damage to the surrounding tissue where the dose was injected; and
- A physician or physician designee will see the patient prior to dosing and prior to discharge.

Follow-Up:

Each study participant will be contacted by phone 24–72 hours after they were injected with the investigational agent to confirm their well-being and query them about any new adverse events that may have occurred within 24 hours post-injection.

Repeat Imaging:

Longitudinal imaging studies may be conducted under protocol ¹⁸F-AV-45-A14, with prior sponsor approval and at the discretion of the investigator. In these studies subjects may have up to two imaging sessions within a 12 month timeframe. Procedures for each day will be identical to those described above.

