7.7.2. Adverse Event Definitions

Adverse Events (AE)

An AE is any undesirable experience occurring to a subject during a clinical trial, whether or not considered related to the investigational product.

For reporting purposes, Avid will distinguish among pre-existing conditions, trial-emergent AEs, and treatment-emergent AEs. The end of study for the purpose of adverse event reporting is defined as 24 hours after administration of florbetapir F 18 injection.

Pre-existing conditions (i.e., undesirable experiences, signs, or symptoms that begin prior to the Screening Visit) will be recorded on the medical history and/or physical exam pages. These conditions will not be entered on the AE pages unless they worsen in intensity or frequency after the Screening Visit and before the Imaging Visit.

Trial-emergent AEs are undesirable experiences, signs or symptoms that begin, or worsen in intensity or frequency, on or after the Screening Visit, and prior to administration of study drug at the imaging visit. These will be recorded on the AE pages.

Treatment-emergent AEs are undesirable experiences, signs, or symptoms that begin or worsen in intensity or frequency at the time of or after the administration of study drug, defined in this protocol as 24 hours after florbetapir F 18 injection. These will be recorded on the AE pages.

Serious Adverse Event (SAE)

An SAE is any AE from this study that results in one of the following outcomes or constitutes one of the following events:

- Death:
- Initial or prolonged inpatient hospitalization (other than that required by protocol; "social hospitalization" or any hospitalization for non-medical reasons does not constitute an SAE);
- A life-threatening experience (that is, immediate risk of dying);
- Persistent or significant disability/incapacity;
- Congenital anomaly/birth defect;
- Occurrence of seizure or seizure-like event:
- Considered significant by the investigator for any other reason.

Important medical events that may not result in death, be life-threatening, or require hospitalization may be considered serious adverse drug events when, based upon appropriate medical judgment, they may jeopardize the patient and may require medical or surgical intervention to prevent one of the outcomes listed in this definition.

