Serious adverse event (SAE) collection begins after the patient has signed informed consent and has received the investigational product. An SAE spontaneously reported to have occurred within 24 hours of florbetapir F 18 administration will be reported, regardless of the investigator's opinion of causation. Thereafter, SAEs are not required to be reported unless the investigator feels the events were related to either investigational product or drug delivery system, or a protocol procedure

Unexpected Adverse Event

An unexpected AE is an AE not previously reported or an AE that occurs with specificity, severity or frequency that is not consistent with the current investigator's brochure.

Relationship to Investigational Product

The assessment of the relationship of an AE to the administration of the study drug (remote, possible, and probable) is a clinical decision based on all available information at the time of the completion of the CRF. The following definitions of the relationship between the study drug and the AE (including SAEs) should be considered:

• Remote (unlikely, doubtful, improbable):
Another cause (concomitant drugs, therapies, complications etc.) is probable.

• Possible:

The time course between the administration of the study medication and the occurrence or worsening of the AE is consistent with a causal relationship but another cause (concomitant drugs, therapies, complications etc.) cannot be ruled out;

or

The time course between the administration of the study medication and the occurrence or worsening of the AE is not consistent with a causal relationship but no alternative cause can be identified.

• Probable:

The time course between the administration of the study medication and the occurrence or worsening of the AE is consistent with a causal relationship and no other cause can be identified (concomitant drugs, therapies, complications etc.).

If the Investigator is unable to assess causality, the AE should be considered "Possible" by definition and not "Remote".

Intensity/Severity of an Adverse Event

In addition to assessing the relationship of the administration of the investigational product to AEs, an assessment is required of the intensity (severity) of the event.

The following classifications should be used:

Mild:

A mild AE is an AE, usually transient in nature and generally not interfering with normal activities.

• Moderate:

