7.7.4. Reporting of Serious Adverse Events

Study site personnel must alert Eli Lilly or its designee of any SAE within 24 hours of investigator awareness of the event via a sponsor-approved method. Alerts issued via telephone are to be immediately followed with official notification on study-specific SAE forms.

Serious adverse events occurring after a subject has taken the last dose of investigational product will be collected 24 hours after the last dose of investigational product, regardless of the investigator's opinion of causation. Thereafter, SAEs are not required to be reported unless the investigator feels the events were related to either investigational product or drug delivery system, or a protocol procedure.

If a patient experiences an SAE after signing informed consent, but prior to receiving investigational product, the event will NOT be collected unless the investigator feels the event may have been caused by a protocol procedure. Previously planned (prior to signing the ICF) surgeries should not be reported as SAEs unless the underlying medical condition has worsened during the course of the study.

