11.2 Trial Flow Chart

Evaluations	Screen	Pre-dose	Dose	Injection Circulation (0 – 50 minutes) ³	Continuous PET Imaging 10 minutes	End of Imaging	24-72 hours post injection
Signed Consent	X						
Medical / Disease History	×						
Concomitant Meds	×	×					
MMSE	×						
Physician Visit	×	Xı				\mathbf{X}_1	
Vital Signs		×				:	
Urine Pregnancy Test	×	×					
Florbetapir F 18 Administration			X				
PET Imaging²					Continuous 10 minute scan - 50 minutes after dose injection		
Follow-up Phone Call							X
Adverse Event Assessment	×	×	×	X	X	X	X^3
	.	-		1	The state of the s		

A physician designee may see the subject prior to injection and at discharge on imaging day.

At the imaging visit body weight will be measured with the subject lightly clothed.

² Sites with dynamic PET acquisition capabilities may elect to acquire a 20 minute acquisition, beginning 30 to 50 minutes post injection. Sites may elect additional imaging timepoints with prior sponsor approval

³ Collect information about any new adverse events that may have occurred within 24 hours post-injection

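### The SAP counts treatment-emergent AEs to 48 hours although the protocol defines and asks about them only to 24 hours, and its later-month partial-date rule contradicts the SAP's own 48-hour limit

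*SAP*

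**What the plan says.** SAP 10.1 defines a treatment-emergent AE as one that begins or worsens "at the time of or after the administration of study drug, and within 48 hours since study drug injection".

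Protocol 7.7.2 sets the treatment-emergent period at 24 hours after injection. It closes AE reporting at the same point: "The end of study for the purpose of adverse event reporting is defined as 24 hours after administration of florbetapir F 18 injection". Protocol 7.1 tells the caller to "query them about any new adverse events that may have occurred within 24 hours post-injection", and footnote 3 of the flow chart in Protocol 11.2 repeats the limit: "Collect information about any new adverse events that may have occurred within 24 hours post-injection". Under Protocol 7.7.4, SAEs after dosing "will be collected 24 hours after the last dose of investigational product, regardless of the investigator's opinion of causation". After that, Protocol 7.7.2 says: "Thereafter, SAEs are not required to be reported unless the investigator feels the events were related" to the product, the delivery system or a protocol procedure.

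SAP 5.3 describes the call differently, as made "approximately 24-48 hours after the imaging session to confirm their well-being and query them about any new adverse events", with no 24-hour limit on the question. SAP 10.5 also uses a 24-48 hour call to mark the end of study. The SAP's own flow chart (Section 4) gives "24-72 hours post injection", which matches the 24-72 hours of Protocol 7.1.

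SAP 10.1.2 covers AEs with a known onset month but no day. If that month is later than the injection month, the event is treatment-emergent without further condition. If it is the injection month, the event is treatment-emergent unless a complete end date shows that it stopped before the injection date.

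**The concern.** SAP Sections 3 and 9 limit the analysis to safety, assessed through reported AEs. Imaging, vital signs, laboratory data and concomitant medications are not summarised. The TEAE tables are therefore the main result, and their numerator depends on the window.

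Two things look wrong. First, the analysis window is twice as long as the period over which sites were told to collect AEs. A percentage labelled as 48-hour incidence would combine events that every subject was asked about (0-24 hours) with events that reached the database incidentally (24-48 hours), all over the full safety population. Second, the partial-date rule counts events whose recorded month may already exclude the 48-hour window.

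As an estimate of true 48-hour incidence, the first problem pushes the figure down and the second pushes it up. The documents do not let one say which dominates.

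**Working it through.** The plan states no figure to reproduce. The check sets the definitions side by side and then uses calendar arithmetic.

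**Step 1. The two documents compared**

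| Item | Protocol | SAP |
|---|---|---|
| TEAE window | to 24 h (7.7.2) | to 48 h (10.1) |
| End point | AE reporting ends at 24 h (7.7.2) | study ends at the 24-48 h call (10.5) |
| Call timing | 24-72 h (7.1) | 24-48 h (5.3, 10.5); 24-72 h (Section 4) |
| Question at the call | first 24 h only (7.1, 11.2) | any new AEs (5.3) |
| SAEs after 24 h | required only if judged related (7.7.2, 7.7.4) | no collection rule |

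The protocol therefore has no routine question covering hours 24-48.

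**Step 2. Would the call cover 48 hours if the question had no limit?** Assume that calls are spread evenly over their window. The share made before 48 h has passed is (48 − earliest) / (latest − earliest).

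- Protocol call, 24-72 h after injection: (48 − 24) / (72 − 24) = 24/48 = 50%.
- SAP 5.3 call, 24-48 h after imaging. Imaging starts about 50 min after injection and lasts 10 min, so it ends about 1 h after injection and the call falls at 25-49 h: (48 − 25) / (49 − 25) = 23/24 = 96%.

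On either schedule many calls would come before the 48-hour window closes, so even the SAP's own description of the call does not give full 48-hour follow-up.

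**Step 3. When can a later-month onset lie inside the window?** For an injection at clock hour t (0 to 23) on the k-th day from the end of a month (k = 1 is the last day), the next month starts 24k − t hours later.

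- k = 1: 1 to 24 h
- k = 2: 25 to 48 h
- k = 3: 49 to 72 h

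A later-month onset can thus lie within 48 h only for k = 1 or 2, which is 2 × 12 = 24 of 365 calendar dates. It can lie within 24 h only for k = 1, which is 12 of 365. On the other 365 − 24 = 341 dates the recorded month alone rules out 48 hours, yet SAP 10.1.2 counts the event. Example with assumed values: injection at 12:00 on 10 March and onset recorded as April. The earliest possible onset is 22 × 24 − 12 = 516 h after injection, and the event is still classed as treatment-emergent.

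**Step 4. How would such an event arise?** An onset learned at a call made by 72 h can fall in a later month only for k = 1, 2 or 3, and for two of those three it can still lie within 48 h. Clear misclassification therefore comes mainly from late or spontaneous reports with a missing onset day.

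**Step 5. Two sessions.** Protocol 7.1 allows up to two imaging sessions within 12 months. Neither SAP 10.1 nor 10.1.2 names the reference injection. With assumed injections in March and September, a fully dated AE one day after the September injection is outside 48 hours of the first and inside 48 hours of the second. A month-only September onset is later-month from the first and same-month from the second. The class depends on a choice that the SAP does not state.

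**The case against.** The strongest reply is that the harm is small and errs on the cautious side. The 48-hour window contains the whole 24-hour window, so no protocol-defined TEAE is lost, provided each injection opens its own window. There is no comparison or error rate to distort, and SAP 10.1.1 lists all AEs. Protocol 5.1 also says that AEs are not collected between the first follow-up call and a second session, which leaves few routes for a long-delayed event to reach the database. All of this stands. It limits the size of the problem but does not reconcile the definitions.

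It can also be said that SAP 5.3 has the caller ask about any new AE, and that Protocol 10.7 wants every AE during the trial recorded. Neither fills the gap. Protocol 7.7.2 ends the trial at 24 hours for AE reporting, and an analysis plan dated May 2018 cannot add a question that the February 2013 protocol did not put to sites.

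A reader might infer that the same-month rule is equally wrong. It is not: the injection month always contains the injection day, so a month-only onset in that month can never exclude the window, and counting it is a defensible conservative choice. A reader might also want the window recast in study days, on the view that only dates are recorded. The protocol gives start and stop dates only as examples of AE detail, and the CRF is not among the documents, so whether onset times exist is unknown.

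**Conclusion.** The point holds and should be fixed. The SAP's TEAE window differs without explanation from the protocol's, its second 24 hours were not systematically solicited, and the later-month rule in SAP 10.1.2 contradicts the limit in SAP 10.1.

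The number of affected events is unknown and probably small, since the documents give no AE counts or timing. The 341 of 365 dates (93.4%) in the calendar check is a share of possible injection dates; a reader might take it as a misclassification rate, but it says nothing about how many events have a missing onset day. Nor do the documents support a claim that the TEAE tables are invalid or that events are hidden.

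The mismatch between the 24-48 and 24-72 hour calls is a wording inconsistency and does not change the TEAE definition. The conclusion assumes that sites collected AEs as Protocol Amendment 3 instructs. The calendar result assumes nothing beyond an injection at some hour of the day.

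**What to change.** 1. Reconcile Protocol 7.7.2 and SAP 10.1 to one TEAE window. Either base the main table on the protocol's 24 hours and show later-onset events separately, or keep 48 hours and footnote that hours 24-48 were not systematically solicited.
2. In SAP 10.1.2, class a later-month partial onset as treatment-emergent only if the chosen window from injection reaches into that month; otherwise only list it. Keep the same-month counting rule, but flag those events as imputed.
3. For subjects with two sessions, apply the window to the most recent injection before onset.
4. As a minor point, align the call timing in SAP 5.3 and 10.5 with Protocol 7.1 and the SAP flow chart.

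The cost is a few lines of SAP wording, a window flag and an imputation flag, with no new data. The downside is that the TEAE count may fall slightly; the events removed remain in the listing.

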10.1.1. Summaries of Adverse Event Incidence Rates for All Patients

All treatment-emergent AEs will be presented in a summary table, by SOC and preferred term. At each level of summarization, a subject will only be counted once per SOC or preferred term. For example, if a subject reports multiple TEAEs with the same SOC, then that SOC will only be incremented by one. As with the SOC, if a subject reports multiple AEs with the same preferred term, then that preferred term will only be incremented by one since subject counts will be presented. AEs will be presented in descending order of frequency. An additional table will present TEAEs in descending frequency by preferred term only. TEAEs will also be summarized by relationship to study drug, and by severity.

All AEs will also be presented in a listing.

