10.1.2. Missing and Partial AE Onset Dates

In the event that only a partial end date (month/year) is available, and month/year occurs before that of study drug injection date, the adverse event will be considered as non-treatment-emergent. However, if the onset date is a partial date (month/year) and month/year occurs on or after that of study drug injection date, the following cases will be considered:

- If month/year of the onset date is greater than the month/year of study drug injection date, the adverse event will be considered treatment-emergent;
- If month/year of the onset date is equal to the month/year of study drug injection date, and the end date is present, the end date will be used to determine when the adverse event

resolved. If the end date is on or after study drug injection date, the adverse event will be considered treatment-emergent; otherwise, if the adverse event stopped before study drug injection date, then it will not be treatment-emergent;

- If month/year of the onset date is equal to the month/year of study drug injection date, and the end date is a partial date, the adverse event will be considered treatment-emergent.

10.1.3. Summaries of Adverse Incidence Rates for Serious Adverse Events (SAE), Adverse Event Dropouts, and Death

A serious adverse event (SAE) is an AE that is fatal or life-threatening, or results in hospitalization, prolongation of hospitalization, persistent or significant disability/incapacity, or a congenital anomaly/birth defect. A life-threatening AE is an AE that, in the view of the investigator, places the subject at immediate risk of death from the reaction as it occurred. Important medical events that may not result in death, be life-threatening, or require hospitalization may be considered SAEs when, based upon appropriate medical judgment, they may jeopardize the subject or subject and may require medical or surgical intervention to prevent one of the outcomes listed in this definition.

If there are any SAE, they will be presented by system organ class and preferred term in a table and a listing. All AEs collected with an outcome of “Fatal” will be presented in a listing.

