10.5. Study Termination Status

For this protocol, the end of study is defined as the completion of 24-48 hours follow up phone call post ¹⁸F-florbetapir scan. The reason for study termination will also be summarized in disposition table. The primary reasons for study termination include: completed study, lost to

follow-up, consent withdrawn, administrative decision, and others.

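### Does the SAP need its own rules for subjects who were injected twice?

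*SAP*

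**What the plan says.** Protocol 5.1 and 7.1 (Repeat Imaging) allow a subgroup up to two imaging sessions in a 12-month period, if the sponsor approves and the investigator agrees. Each session follows the same procedures, so a second session brings a second injection and a second follow-up call. Protocol 5.1 adds that adverse events are not collected between the first follow-up call and the second session.

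The SAP is limited to a descriptive safety report. Its relevant rules are:

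- Section 6: "Date of florbetapir administration is defined as study day 1".
- Section 6.1.3: the safety population is "all subjects who received at least one injection of florbetapir".
- Section 7: "Disposition of subjects including the number and percentage of subjects will be displayed based on Safety population".
- Section 10.1: an adverse event is "any undesirable experience occurring to a subject after an injection of florbetapir F 18". It is treatment-emergent if it begins or worsens "at the time of or after the administration of study drug, and within 48 hours since study drug injection".
- Section 10.1.1: subjects, not events, are counted once per system organ class or preferred term. "All AEs will also be presented in a listing".
- Section 10.1.2: partial dates are compared with the injection date, for example "If month/year of the onset date is equal to the month/year of study drug injection date".
- Section 10.5: "the end of study is defined as the completion of 24-48 hours follow up phone call" after the scan. The reason for termination goes into the disposition table.

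No SAP section refers to a second session, injection or call, and the SAP flow chart shows one session.

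**The concern.** Every date rule in the SAP is written as if each subject had one injection date. For a subject with two, the choice of date could decide whether an event counts as treatment-emergent. If a programmer stored only the first date, events after the second injection would fall outside the window. If only the second were stored, events after the first would precede it.

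Disposition raises a similar question. A subject who completes the first call but cannot be reached after the second scan could be put under either completed or lost to follow-up.

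Finally, the report's purpose is to describe safety in exposed subjects, yet no named table shows how many were exposed twice. At stake would be undercounted adverse events, an arbitrary disposition entry, and a reader unable to tell subjects from injections.

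**Working it through.** The plan states no figure for repeat imaging, so there is none to reproduce. The check traces the rules for a subject with two injections and then gauges the scale.

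**1. Treatment-emergent window, complete dates.** Take injections in month 1 and month 12.

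| Event | First injection only | Second injection only | Each injection |
|---|---|---|---|
| 10 hours after injection 1 | in window | before injection, out | in window |
| 10 hours after injection 2 | about 11 months late, out | in window | in window |

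Only the single-date readings lose an event, and the documents point away from both. Section 6.1.3 expects that there may be more than one injection. Section 10.1 defines an adverse event relative to an injection, not the first one. The protocol repeats its procedures at the second session and suspends adverse event collection only between the first call and that session, so second-session events are meant to be reported. Under the per-injection reading no fully dated event is lost, and a subject still counts once per term, so the incidence is a valid any-injection incidence.

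**2. Study day.** The treatment-emergent rule runs in hours from injection and does not use study day. The choice of day 1 for a second session affects labelling only.

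**3. Partial dates.** Apply section 10.1.2 to each injection, and call the event treatment-emergent if it qualifies against either. Take injections on 5 and 28 January, onset recorded as January, and end date 7 January. Against 5 January the months match and the event ended on or after injection, so it is treatment-emergent. Against 28 January it ended before injection, so it is not. The either-injection reading keeps it.

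In the other direction, a month-only onset in month 12 is later than the month of injection 1, so it counts as treatment-emergent whenever it fell in that month. That errs towards inclusion. The same absence of a 48-hour check affects once-injected subjects, so it is a separate matter.

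**4. Disposition.** Section 10.5 lists primary reasons for termination, which implies one status per subject. Protocol 5.5 has the site record the date and reason for discontinuation on the CRF. Protocol 5.1 speaks of a first call and a second session, so a subject having a second scan is still in the study after the first call. The natural entry is the status after the last session.

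**5. Scale.** Inputs: N of about 1,800 (Protocol 5.1); the re-imaged fraction is an assumption because no document gives it. Second injections n = fraction × N. Share of all injections = n/(N + n). Zero-event one-sided 95% upper limit on risk = 1 − 0.05^(1/n).

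| Assumed fraction | n | Share of injections | Zero-event upper limit |
|---|---|---|---|
| 1% | 18 | 18/1,818 = 1.0% | 15.3% |
| 2% | 36 | 36/1,836 = 2.0% | 8.0% |
| 5% | 90 | 90/1,890 = 4.8% | 3.3% |
| 10% | 180 | 180/1,980 = 9.1% | 1.7% |

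With few re-imaged subjects, a table by exposure number would say little. The disposition ambiguity touches only those among the n whose two sessions ended differently.

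**The case for a change.** The best case for a change is that it costs little: a sentence in each of four SAP sections and two table rows would remove all doubt. The SAP is indeed silent, its instruction to read it with the protocol supplies no analysis rule for two injections, and its planned listings are not specified closely enough to guarantee that second injections appear. All of that stands.

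A sharper point concerns partial dates. If an event after injection 1 has both onset and end recorded only as month 1, the opening sentence of section 10.1.2, tested against a month-12 injection, makes it non-treatment-emergent. The last bullet, tested against injection 1, makes it treatment-emergent. Testing each injection therefore needs a way to combine two answers. The AE definition in section 10.1 supplies it: an event that qualifies after an injection qualifies.

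A written rule is not free of risk either. The obvious one, linking each event to the most recent injection by month, would select 28 January in the example above and drop a possible treatment-emergent event of the 5 January injection. The protocol sets no minimum interval between sessions, so that case cannot be excluded.

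The exposure count is useful context, but incidence per subject in the safety population does not depend on it. The SAP deliberately keeps its output short and leaves concomitant medications and vital signs to post hoc tables if the findings call for them. A count of injections can be handled the same way.

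**Conclusion.** The observation is accurate, but it describes a gap that analysts fill sensibly, not a fault in the analysis. On the per-injection reading that the SAP's own definitions support, the loss of fully dated treatment-emergent events is zero. With the either-injection reading, the partial-date rules lean towards counting an event. End-of-study status follows from the reason the site records, taken after the last session. The missing exposure count leaves the planned incidences sound.

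This rests on three assumptions: that the database holds both injection dates, which cannot be confirmed because the CRF is not shown; that the programmers use both; and that disposition has one entry per subject. The number of re-imaged subjects is not given, so the practical consequence is unknown and may be nil. The report is descriptive, tests no hypothesis, and keeps all adverse events in a listing. No change to the plan is called for.
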